16.3 Appendix III: Transthoracic Echocardiography Acquisition Guidelines

[REDACTED]	[REDACTED]	[REDACTED]	[REDACTED]	[REDACTED]
[REDACTED]	[REDACTED]	[REDACTED]	[REDACTED]	[REDACTED]
[REDACTED]	[REDACTED]	[REDACTED]	[REDACTED]	[REDACTED]
[REDACTED]	[REDACTED]	[REDACTED]	[REDACTED]	[REDACTED]

16.4 Appendix IV: Revision History

16.5 Appendix V: Protocol Summary

Trial Name and Number	MitraClip China PMS CRD956-PMS
Title	MitraClip China PMS: A Prospective, Multi-Center, Single-Arm, Post Market Study of the MitraClip System for the Treatment of Symptomatic Mitral Regurgitation in China (CRD956-PMS)
Objectives	To confirm the evidence of safety and efficacy of MitraClip system in Chinese subjects with a post market setting.
Devices	MitraClip System (CDS0601-NTR, CDS0601-XTR, SGC0301)
Targeted number of subjects to receive study device	A minimum of 50 subjects and a maximum of approximately 100 subjects at up to 10 sites in China.
Study Design	
 Prospective, multi-center, single-arm, post market study Subjects will be evaluated at baseline, index procedure, discharge, 30 days and 1 year
Primary Endpoints	
 Acute Procedural Success (APS) Freedom from Major Adverse Event (MAE) rate at 30 days
Descriptive Endpoints	
Clinical Endpoints:
 
The following descriptive clinical endpoints will be assessed at all scheduled office visits.
 
 All-cause mortality Freedom from the components of MAE NYHA Functional Class Kansas City Cardiomyopathy Questionnaire (KCCQ) Quality of Life (QoL) scores Six Minute Walk Test (6MWT) distance Mitral valve surgery (including type of surgery), including reason for intervention Additional MitraClip System intervention, including reason for intervention Number of hospitalizations and reason for hospitalization (i.e. heart failure, cardiovascular, non-cardiovascular) in study period Device-related complications: defined as a composite of single leaflet device attachment (SLDA), device embolization, clinically significant iatrogenic septal defect or mitral stenosis that requires intervention Major bleeding

	
Device and Procedure-Related Endpoints:
 
 • Implant Success Rate: Defined as the rate of successful delivery and deployment of one or more MitraClip devices and retrieval of the delivery catheter • Device Procedure Time: Defined as the time elapsed from the start of the transseptal procedure to the time the Steerable Guide Catheter is removed • Total Procedure Time: defined as the time elapsed from the first of any of the following: intravascular catheter placement, anesthesia or sedation, or transesophageal echocardiogram (TEE), to the removal of the last catheter and TEE • Device Time: Defined as the time the Steerable Guide Catheter is placed in the intra-atrial septum until the time the MitraClip Delivery System (CDS) is retracted into the Steerable Guide Catheter • Fluoroscopy Time: defined as the total minutes of exposure to fluoroscopy during the MitraClip procedure • Length of stay in Intensive Care Unit/Critical Care Unit/Post-Anesthesia Care Unit (ICU/CCU/PACU) • Length of hospital stay for index MitraClip procedure 
Echocardiographic Endpoints:
 
The following descriptive echocardiographic endpoints will be assessed at all scheduled office visits.
 
 • MR Severity Grade • Effective Regurgitant Orifice Area • Regurgitant Volume (RV) • Regurgitant Fraction (RF) • Left Ventricular End Diastolic Volume (LVEDV) • Left Ventricular End Systolic Volume (LVESV) • Left Ventricular End Diastolic Dimension (LVEDD) • Left Ventricular End Systolic Dimension (LVESD) • Left Ventricular Ejection Fraction (LVEF) • Right Ventricular Systolic Pressure (RVSP) • Mitral Valve Area (MVA) • Mean Mitral Valve Pressure Gradient (MVG) • Systolic Anterior Motion of the mitral valve (present or absent) • Forward Stroke Volume (FSV) • Cardiac Output (CO) • Cardiac Index (CI)
Subject Follow-up	Subjects will have scheduled office visit evaluations for assessment of study endpoints at hospital discharge, 30 days and 1 year.

Inclusion Criteria	
• Subject is eligible to receive the MitraClip per the current approved MitraClip System IFU• Subject is 18-year-old or above• Subject who gives consent for study procedure
Exclusion Criteria	
• Subject cannot tolerate procedural anticoagulation or anti-platelet regimen• Subject with active endocarditis of mitral valve• Subject with rheumatic mitral valve disease• Subject with echocardiographic evidence of intracardiac, IVC or femoral venous thrombus• Subject is unlikely to survive the protocol follow up period of 12-months after device implant• Subject has insufficient or lost ability to maintain their will and rights• Subject is illiterate• Subject participates in another clinical study that may impact the follow-up or results of this study

1.0 SYNOPSIS OF STUDY DESIGN

1.1 Purpose of the Statistical Analysis Plan

This statistical analysis plan (SAP) is to provide a detailed and comprehensive description of the planned methodology and analysis to be used for Clinical Investigation Plan (CIP) [REDACTED], the MitraClip China post market study clinical investigation. This plan is based on [REDACTED] of the Clinical Investigation Plan.

1.2 Clinical Investigation Objectives

To confirm the evidence of safety and efficacy of MitraClip System in Chinese symptomatic MR subjects with a post market setting.

1.3 Clinical Investigation Design

The MitraClip China PMS is a prospective, multi-center, single-arm, post market study designed to collect data on use of the MitraClip System in Chinese subjects. A minimum of 50 subjects and a maximum of approximately 100 will be registered up to 10 sites in the MitraClip China PMS. Follow-up of subjects registered in the MitraClip China PMS will occur at discharge, 30 days and 1 year. [REDACTED]

1.4 Endpoints

1.4.1 Primary Endpoint(s)

Two primary endpoints are designed for the MitraClip China PMS.

- Acute procedural success (APS). APS is defined as successful implantation of the MitraClip device(s) with resulting MR severity of 2+ or less as determined by the ECL assessment of a discharge echocardiogram (30-day echocardiogram will be used if discharge echocardiogram is unavailable or uninterpretable). Patients who die or who undergo mitral valve surgery before discharge are an APS failure.
- Freedom from major adverse event (MAE) at 30 days. MAE is a composite of death, stroke, MI, renal failure, and non-elective cardiovascular surgery for device or procedure related adverse events occurring after the femoral vein puncture for transseptal access.

1.4.2 Descriptive Endpoint(s)

Clinical Endpoints

The following descriptive clinical endpoints will be assessed at all scheduled office visits:

- All-cause mortality
- Freedom from the components of MAE
- NYHA Functional Class
- Kansas City Cardiomyopathy Questionnaire (KCCQ) Quality of Life (QoL) scores
- Six Minute Walk Test (6MWT) distance
- Mitral valve surgery (including type of surgery), including reason for intervention
- Additional MitraClip System intervention, including reason for intervention
- Number of hospitalizations and reason for hospitalization (i.e., heart failure, cardiovascular, non-cardiovascular)

Statistical Analysis Plan

- Device-related complications: defined as a composite of single leaflet device attachment (SLDA), device embolization, clinically significant iatrogenic septal defect or mitral stenosis that requires intervention
- Major bleeding

Device and Procedure-Related Endpoints

- Total Procedure Time: defined as the time elapsed from the first of any of the following: intravascular catheter placement, anesthesia or sedation, or transesophageal echocardiogram (TEE), to the removal of the last catheter and TEE
- Device Procedure Time: Defined as the time elapsed from the start of the transseptal procedure to the time the Steerable Guide Catheter is removed
- Device Time: Defined as the time the Steerable Guide Catheter is placed in the intra-atrial septum until the time the MitraClip Delivery System is retracted into the Steerable Guide Catheter
- Fluoroscopy Time: defined as the total minutes of exposure to fluoroscopy during the MitraClip procedure
- Length of stay in Intensive Care Unit/Critical Care Unit/Post-Anesthesia Care Unit (ICU/CCU/PACU)
- Length of hospital stay for index MitraClip procedure

Echocardiographic Endpoints

The following descriptive echocardiographic endpoints will be assessed at all scheduled office visits.

- MR Severity Grade
- Effective Regurgitant Orifice Area
- Regurgitant Volume (RV)
- Regurgitant Fraction (RF)
- Left Ventricular End Diastolic Volume (LVEDV)
- Left Ventricular End Systolic Volume (LVESV)
- Left Ventricular End Diastolic Dimension (LVEDD)
- Left Ventricular End Systolic Dimension (LVESD)
- Left Ventricular Ejection Fraction (LVEF)
- Right Ventricular Systolic Pressure (RVSP)
- Mitral Valve Area (MVA)
- Mean Mitral Valve Pressure Gradient (MVG)
- Systolic Anterior Motion of the mitral valve (present or absent)
- Forward Stroke Volume (FSV)
- Cardiac Output (CO)
- Cardiac Index (CI)

2.0 ANALYSIS CONSIDERATIONS

2.1 **Analysis Populations**

2.1.1 **Attempted Procedure Population (AP)**

Statistical Analysis Plan

2.1.2 Implanted Population (IP)

[REDACTED]

2.2 Statistical Methods

Descriptive analysis will be performed to summarize baseline, APS, clinical and safety event data. Depending on the type of data (e.g., continuous, or categorical), statistical methods described in this section below will be used.

2.2.1 Descriptive Statistics for Continuous Variables

For continuous variables (e.g., age, etc.), results within treatment arm will be summarized with the numbers of observations, means, and standard deviations, with 95% confidence intervals for the means as per the table mockups.

2.2.2 Descriptive Statistics for Categorical Variables

For categorical variables (e.g., gender, etc.), results within treatment arm will be summarized with subject counts and percentages/rates

[REDACTED]

2.2.3 Survival Analyses

Survival analysis will be conducted to analyze time-to-event variables (e.g., all-cause mortality, etc.). Subjects without events will be censored at their last known event-free time point.

[REDACTED]

2.3 Endpoint Analysis

2.3.1 Primary Endpoint(s)

The primary endpoints APS and MAE at 30 days. The primary endpoints analysis will be performed on AP population, and IP population (if applicable).

[REDACTED]

2.3.2 Descriptive Endpoints

The analyses for the descriptive endpoints will be performed using the methods described in Section 2.2 for on the AP and IP populations (if applicable).

2.4 Sample Size Calculations

A minimum of 50 subjects and a maximum approximately 100 subjects will be registered at up to 10 sites.

[REDACTED]

Statistical Analysis Plan

2.5 Interim Analysis

No formal interim analyses are planned for this study. As such, no formal statistical rule for early termination of the trial is defined. Interim study reports with descriptive analysis may be produced for regulatory or publication purposes.

2.6 Timing of Analysis

The primary endpoint analyses will be performed when all registered subjects complete their 30-day follow-up.

2.7 Subgroups for Analysis

Descriptive or exploratory analyses may be performed for specific subgroups.

2.8 Handling of Missing Data

All analyses will be based on available data with missing data excluded. Any unused or spurious data will be noted as appropriate in the final report.

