Freedom from mitral valve surgery in MitraClip patients at 12 months, 24 months, 3 years, 4 years, and 5 years was 78.9%, 78.2%, 77.6%, 76.0%, and 74.3%, respectively, and freedom from re-operation in surgery patients was 97.4%, 96.0%, 94.4%, 94.4%, and 92.5%, respectively. Weibull estimates of freedom from death, mitral valve surgery and MR > 2+ at 12 months, 24 months, 3 years, and 4 years was 60.8%, 55.4%, 52.0%, and 49.5%, respectively, in MitraClip patients; and freedom from death, re-operation and MR >2+ was 89.0%, 82.6%, 77.6%, and 73.3%, respectively, in surgery patients. While there was an initial drop in freedom from death, mitral valve surgery and MR > 2+ due to MitraClip patients undergoing mitral valve surgery within 12 months of the MitraClip procedure, these patients did not experience any worse deterioration in durability than surgery patients beyond 12 months.

Significant and meaningful clinical benefits were observed in both MitraClip and surgery patients, which were sustained through 5 years:

- MR reduction to 2+ or less at 5 years was in 82.1% of MitraClip patients and 97.6% of surgery patients
- Reduction in left ventricular end diastolic volume and dimension was observed in both MitraClip and surgery patients, which was sustained through 5 years
- Improvement in NYHA Functional Class was demonstrated in both groups, with 91.5% of MitraClip patients and 97.6% of surgery patients free from NYHA Functional Class III or IV symptoms at 5 years

The results of the EVEREST II RCT demonstrate the continued safety, durability of effectiveness and clinical benefit of the MitraClip device through 5 years. These results are consistent with the expectation of superior safety and reduced effectiveness of the MitraClip device when compared to mitral valve surgery. These results support an overall favorable risk to benefit profile of the MitraClip device through 5 years.

EVEREST II High Risk Registry Design and Results

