4.2 Descriptive Endpoints

Clinical Endpoints

The following descriptive clinical endpoints will be assessed at all scheduled office visits.

- All-cause mortality
- Freedom from the components of MAE
- NYHA Functional Class
- Kansas City Cardiomyopathy Questionnaire (KCCQ) Quality of Life (QoL) scores
- Six Minute Walk Test (6MWT) distance
- Mitral valve surgery (including type of surgery), including reason for intervention

- Additional MitraClip System intervention, including reason for intervention
- Number of hospitalizations and reason for hospitalization (i.e. heart failure, cardiovascular, non-cardiovascular)
- Device-related complications: defined as a composite of single leaflet device attachment (SLDA), device embolization, clinically significant iatrogenic septal defect or mitral stenosis that requires intervention.
- Major bleeding

Device and Procedure-Related Endpoints

- Total Procedure Time: defined as the time elapsed from the first of any of the following: intravascular catheter placement, anesthesia or sedation, or transesophageal echocardiogram (TEE), to the removal of the last catheter and TEE
- Device Procedure Time: Defined as the time elapsed from the start of the transseptal procedure to the time the Steerable Guide Catheter is removed
- Device Time: Defined as the time the Steerable Guide Catheter is placed in the intra-atrial septum until the time the MitraClip Delivery System is retracted into the Steerable Guide Catheter
- Fluoroscopy Time: defined as the total minutes of exposure to fluoroscopy during the MitraClip procedure
- Length of stay in Intensive Care Unit/Critical Care Unit/Post-Anesthesia Care Unit (ICU/CCU/PACU)
- Length of hospital stay for index MitraClip procedure

Echocardiographic Endpoints

The following descriptive echocardiographic endpoints will be assessed at all scheduled office visits.

- MR Severity Grade
- Effective Regurgitant Orifice Area
- Regurgitant Volume (RV)
- Regurgitant Fraction (RF)
- Left Ventricular End Diastolic Volume (LVEDV)
- Left Ventricular End Systolic Volume (LVESV)
- Left Ventricular End Diastolic Dimension (LVEDD)
- Left Ventricular End Systolic Dimension (LVESD)
- Left Ventricular Ejection Fraction (LVEF)

- Right Ventricular Systolic Pressure (RVSP)
- Mitral Valve Area (MVA)
- Mean Mitral Valve Pressure Gradient (MVG)
- Systolic Anterior Motion of the mitral valve (present or absent)
- Forward Stroke Volume (FSV)
- Cardiac Output (CO)
- Cardiac Index (CI)

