5.5 Subject Withdrawal and Discontinuation

Each registered subject shall remain in the study until completion of the required follow-up period; however, a subject's participation in any clinical study is voluntary and the subject has the right to withdraw at any time without penalty or loss of benefit. If the subject decides to withdraw prior to the 1-year follow-up visit, all available data prior to formal documentation of withdrawal from the study must be collected. Conceivable reasons for discontinuation may include, but not be limited to, the following:

- Subject death
- Subject voluntary withdrawal
- Investigator judgment of subject discontinuation
- Subject lost-to-follow-up as described below

Sites must notify the Sponsor of the reason(s) for subject discontinuation. Investigators must also report this to their respective EC as defined by their institution's procedure(s).

No additional follow-up is required or data recorded from subjects once withdrawn from the study, except for the status (deceased/alive).

However, if a subject withdraws from the study due to problems related to the safety or performance of the device under study, the investigator shall ask for the subject's permission to follow his/her status/condition outside of the study.

In case of subject voluntary withdrawal, the site should make attempts to schedule the subject for a final study visit.

Lost-to-Follow-up:

If the subject misses two consecutive scheduled follow-up time points and the attempts at contacting the subject detailed below are unsuccessful, then the subject is considered lost-to-follow-up. Site personnel shall make all reasonable efforts to locate and communicate with the subject (and document these efforts in the source documents), including the following, at each contact time point:

- A minimum of two telephone calls on different days over the specified follow-up windows to contact the subject should be recorded in the source documentation, including date, time and initials of site personnel trying to make contact.
- If these attempts are unsuccessful, the site should send a letter (certified if applicable) to the subject.

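### The visible SAP has no rule for 1-year values recorded after post-discharge mitral valve surgery, so by default they are pooled with the device's own results

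*SAP*

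**What the plan says.** SAP 2.3.2 covers the descriptive endpoints in one sentence: "The analyses for the descriptive endpoints will be performed using the methods described in Section 2.2", applied to the attempted-procedure and implanted populations. For continuous measures, SAP 2.2.1 says "results within treatment arm will be summarized with the numbers of observations, means, and standard deviations", with a confidence interval for the mean. SAP 2.8 adds "All analyses will be based on available data with missing data excluded". None of these three sections shows a redaction, and none mentions re-intervention.

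Protocol 5.5 keeps subjects in the study: "Each registered subject shall remain in the study until completion of the required follow-up period". Mitral valve surgery is not among the discontinuation reasons listed there, although that list is not exhaustive. Under Protocol 6.6, implanted subjects attend at 1 year for echocardiography, NYHA class, KCCQ and six-minute walk. Subjects without an implant are followed for 30 days only. On the echo measures, Protocol 4.2 says "The following descriptive echocardiographic endpoints will be assessed at all scheduled office visits".

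The one visible rule that treats surgery as failure belongs to acute procedural success and stops at discharge: "Patients who die or who undergo mitral valve surgery before discharge are an APS failure" (SAP 1.4.1). Mitral valve surgery and additional MitraClip procedures are separate descriptive endpoints (SAP 1.4.2).

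**The concern.** The study is meant to confirm the safety and efficacy of the MitraClip System, and the 1-year visit is its only scheduled assessment after 30 days. An implanted subject who is operated on after discharge and attends at 1 year provides a measurement that is present, and so counts as available, but that describes a different treatment. After a valve replacement, mitral valve area and mean gradient describe a prosthesis, yet they would be averaged with values from clipped valves.

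For MR grade the direction is predictable. Subjects whose clip has failed are presumably those most likely to be operated on. The protocol's background (1.1.1) reports MR of 2+ or less after surgery in 100% of patients at discharge and 97.6% at 5 years. A poor device result can therefore reappear in the 1-year table as a good one. For left ventricular measures, NYHA class, KCCQ and walk distance, the documents give no basis for sizing the effect.

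**Working it through.** The visible text gives no expected surgery rate, precision or target for any 1-year endpoint, so there is no figure in the plan to reproduce. What follows is a sensitivity calculation for the proportion with MR 2+ or less.

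**Inputs (Protocol 1.1.1, earlier randomized trial of clip against surgery)**
- Device patients at 12 months: 93.7% alive, 78.9% free of mitral valve surgery, and 60.8% free of death, surgery and MR above 2+ (a Weibull estimate).
- Surgery patients at 5 years: 97.6% with MR 2+ or less.
- Implant rate among device patients: 89%.

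**Assumptions**
- Death and surgery are independent.
- The 5-year figure for surgery patients applies at 1 year after surgery that follows a clip.
- The share s of 1-year attendees with earlier mitral surgery is 2%, 5% or 10%. The documents give no value for s.

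**Rate without surgery.** p = 0.608 / (0.937 × 0.789) = 0.8224.

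**Three treatments of the operated subjects**
- Pooled: (1 − s)p + 0.976s
- Set aside: p
- Surgery counted as failure: (1 − s)p

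The excess from pooling is s(0.976 − p) against setting aside, and 0.976s against failure.

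| s | Pooled | Set aside | Failure | Excess vs set aside | Excess vs failure |
|---|---|---|---|---|---|
| 2% | 82.5% | 82.2% | 80.6% | 0.3 points | 2.0 points |
| 5% | 83.0% | 82.2% | 78.1% | 0.8 points | 4.9 points |
| 10% | 83.8% | 82.2% | 74.0% | 1.5 points | 9.8 points |
| 21.1% (upper bound) | 85.5% | 82.2% | 64.9% | 3.2 points | 20.6 points |

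**Why 21.1% is an upper bound.** It is 100% − 78.9%, from a trial in which 11% of device patients received no implant. If all of those had surgery (an assumption), the rate among implanted patients would be (21.1 − 11) / 89 = about 11%.

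**Sensitivity to p.** If every operated subject reaches MR 2+ or less, the excess over setting aside is s(1 − p). It runs from 0.2 points (p = 90%, s = 2%) to 5.3 points (p = 75%, s = 21.1%).

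**Will it arise at all?** The chance of at least one operated subject is 1 − (1 − s)^N. At s = 2% it is 64% for N = 50 and 87% for N = 100. At s = 5% it is 92% and 99%.

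**Scale against sampling error.** Take 50 attendees, 5 of them operated on and all 5 with MR 2+ or less:
- Pooled: 41/50 = 82% (95% exact CI 69% to 91%)
- Set aside: 36/45 = 80% (65% to 90%)
- Surgery as failure: 36/50 = 72% (58% to 84%)

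**The case against.** The strongest reply is that the SAP is silent on this point and does not state a rule. The sentence in SAP 2.8 concerns missing data. Text is redacted in SAP 2.2.2 (categorical variables, hence MR grade and NYHA), 2.2.3 and 2.3.1, and the population definitions are not visible. A rule for categorical endpoints may sit there. That stands as a limit. It does not reach the continuous measures, because SAP 2.2.1, 2.3.2 and 2.8 appear in full.

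Second, surgery and repeat clips are reported as endpoints with reasons, so a reader will see how many occurred. That stands too, but a count elsewhere does not show how many values in each 1-year table are post-surgical.

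Third, the gap against counting surgery as failure is almost the assumed surgery rate itself. Against setting values aside, the shift is small beside the sampling error. Both parts are correct. The documents also list MR severity grade, not a 1-year success rate; the 2+ cut-off used here is borrowed from acute procedural success.

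Two stronger readings are tempting. A reader might infer an inflation of about 21 points. The documents do not support that: the rate behind it includes patients never implanted, who in this study have no required 1-year visit. A reader might also infer that results after a second MitraClip are wrongly credited. They are not a surgeon's result, and the stated objective concerns the MitraClip System, so keeping them is a legitimate system-level summary if declared.

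**Conclusion.** The concern holds in a limited form. On the visible text, values recorded after post-discharge mitral valve surgery in implanted subjects enter the 1-year descriptive summaries by default, unless a redacted passage says otherwise for categorical endpoints. The bias in MR grade favours the device. At assumed surgery rates of 2% to 10%, it is about 0.3 to 1.5 points against setting those values aside and about 2 to 10 points against counting surgery as failure. These sizes rest on background figures from another trial, on independence of death and surgery, and on surgery rates that the documents do not supply.

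The consequence is limited to the interpretation of 1-year descriptive results. Protocol 8 plans no hypothesis tests, and the primary endpoints are unaffected. This is a cheap improvement and not a flaw that threatens the study.

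**What to change.** Add to SAP 2.3.2:

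- Values recorded after mitral valve surgery are set aside from the 1-year device summaries, and the number set aside is shown beside each summary.
- One further 1-year table gives the number of subjects alive, free of mitral valve surgery and with MR 2+ or less. This is needed because setting values aside also drops failed clips from the denominator. The table mirrors the composite that Protocol 1.1.1 uses for the earlier randomized trial. Because it also counts deaths, its figure will be lower than one that counts surgery alone as failure.
- Values after a repeat MitraClip stay in the system-level summary, with the number of such subjects shown.
- The summary of all available data is kept as a supplementary table.

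No new data are needed, since Protocol 6.7 and 11.4 already collect mitral valve surgery and additional MitraClip procedures. The cost is a few lines of SAP text, one extra table and a slightly less favourable 1-year figure. If a redacted section already contains a rule, a cross-reference from 2.3.2 and the counts would be enough for the endpoints it covers.

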- 45% reduction in the 12-month rate of hospitalization for heart failure post-treatment compare with the 12-month rate prior to MitraClip intervention
- Reduction in left ventricular end diastolic volume and dimension, and left ventricular end systolic volume, which was sustained through 5 years
- NYHA Functional Class was improved from approximately 90% of patients in NYHA Functional Class III or IV at baseline to 83.7% free from NYHA Functional Class III or IV symptoms at 5 years

The results of the EVEREST II High Risk Registry demonstrate continued safety, durability of effectiveness and clinical benefit of the MitraClip device through 5 years. These results support an overall favorable risk to benefit profile of the MitraClip device in high surgical risk patients through 5 years.

EVEREST II REALISM Study Design and Results

The objective of the EVEREST II REALISM Continued Access Registry was to collect data on the use of the minimally-invasive catheter-based MitraClip device under “real-world” conditions in high risk and non-high risk patients with moderate-to-severe (3+) or severe (4+) chronic MR. REALISM was a prospective, multi-center, Continued Access Registry. The study enrolled patients in two arms: the high risk and non-high risk arms. Eligibility for the Non-High Risk arm was the same as for the EVEREST II RCT and that for the High Risk arm was the same as for the HRR.

Enrollment in the Continued Access REALISM study was initiated on January 22, 2009. A total of 899 patients (628 High Risk, 271 Non-High Risk) were enrolled and treated in the EVEREST II REALISM Continued Access Study. Enrollment in the Non-High Risk arm of

the study concluded on April 14, 2011 and enrollment in the High Risk arm concluded on December 19, 2013.

All-cause mortality and major adverse event rates at 30 days in the REALISM High Risk arms were 4.1% and 15.6% respectively. The 12 months all-cause mortality and major adverse event rates were 23.4% and 35.5% respectively.

The severity of MR consistently remained mild to moderate (2+ or less) for a majority (>80%) of the patients and the NYHA Functional Class were Class I/II for a majority (>80%) of the patients through 5 years.

The safety and durability results of the REALISM High Risk arms provide further evidence that the “real-world” use of the MitraClip device continues to perform as expected based on the EVEREST II Randomized Controlled Trial and High Risk Registry.

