8 STATISTICAL CONSIDERATIONS

This is a post market study of consecutive consented, eligible subjects who have attempted treatment of the MitraClip System at participating sites. No pre-specified hypothesis tests are planned for the MitraClip China PMS. The following section describes the statistical methods for the MitraClip China PMS.

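### The available-data rule in SAP 2.8 gives no visible treatment of death, so the 1-year KCCQ, NYHA, 6MWT and MR results describe only subjects alive, implanted and assessed

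*SAP*

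**What the plan says.** SAP 2.8 sets one rule: "All analyses will be based on available data with missing data excluded". It makes no separate provision for death, withdrawal or a missed visit.

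SAP 2.3.2 sends the descriptive endpoints to the methods of SAP 2.2, on the AP and (if applicable) IP populations. Continuous variables are "summarized with the numbers of observations, means, and standard deviations, with 95% confidence intervals for the means as per the table mockups". For categorical variables, "results within treatment arm will be summarized with subject counts and percentages/rates"; the visible text gives no denominator. The endpoints in SAP 1.4.2 include "Kansas City Cardiomyopathy Questionnaire (KCCQ) Quality of Life (QoL) scores", NYHA class, six-minute walk distance and MR grade, all assessed at office visits.

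SAP 3.1 summarises baseline for the subjects enrolled. It names echocardiographic measurements and leaves the list open-ended. Protocol 6.6 follows subjects without an implant for 30 days only, so they have no 1-year visit.

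Other parts of the plan do deal with death or early exit. APS counts death or mitral surgery ahead of discharge as failure (SAP 1.4.1). Time-to-event variables are censored (SAP 2.2.3). All-cause mortality is an endpoint, and early terminations are tabulated by visit (SAP 3.3).

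**The concern.** A subject who dies in month five has no KCCQ score, NYHA class, walk distance or MR grade at 1 year. Under SAP 2.8 that subject leaves the 1-year summary but stays in the baseline summary. The same happens to a subject in whom no clip could be implanted. Part of any difference between the baseline and 1-year columns may then reflect who is measured rather than how subjects changed. A percentage in NYHA I/II at 1 year may also be read as the result for everyone treated.

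Two small series cited in Protocol 1.1.1 show the mechanism, though not its size. In the report of three early cases in China, one patient's MR and cardiac function worsened before death at day 162; under SAP 2.8 such a patient would be absent from every 1-year functional and MR summary. In the 20-patient series, one patient died within 30 days after MR was not successfully treated, yet the 30-day result describes all patients as NYHA I or II.

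The study is meant to confirm safety and efficacy for a regulatory report, and 1 year is its last scheduled visit. These summaries will be its evidence on whether benefit lasts.

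**Working it through.** The documents give no figure to reproduce on this point. Protocol 8 says "No pre-specified hypothesis tests are planned for the MitraClip China PMS", and the visible part of SAP 2.4 gives only a range: "A minimum of 50 subjects and a maximum approximately 100 subjects will be registered at up to 10 sites". The check is simple arithmetic.

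**Inputs from Protocol 1.1.1**
- 12-month mortality m:
  - 6.3% = 100% − 93.7% (EVEREST II RCT, device patients)
  - 23.4% (REALISM High Risk arm: "The 12 months all-cause mortality and major adverse event rates were 23.4% and 35.5% respectively")
  - 24.6% = 100% − 75.4% (High Risk Registry)
- Implant rate r: 89% (EVEREST II RCT) and 96.2% (High Risk Registry)

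**Assumed inputs**
- p = 80% of observed subjects in NYHA I/II at 1 year. REALISM reports more than 80% through 5 years.
- d = 0 to 20 KCCQ points, the amount by which the baseline mean of later decedents lies below that of survivors. The documents give no value.

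**Step 1. Expected deaths before the 1-year visit, N × m**
- N = 50: 50 × 0.063 = 3.2 to 50 × 0.246 = 12.3
- N = 100: 6.3 to 24.6

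**Step 2. Largest share of registered subjects who could have 1-year data, r × (1 − m)**
- Low end: 0.89 × 0.754 = 67.1%
- High end: 0.962 × 0.937 = 90.1%

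This combines rates from different studies, assumes the same mortality in implanted subjects, and comes before withdrawals and missed visits.

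**Step 3. Share of all subjects alive and in NYHA I/II, p × (1 − m)**

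| m | Calculation | Share of all subjects | Gap from 80% (percentage points) |
|---|---|---|---|
| 6.3% | 0.80 × 0.937 | 75.0% | 5.0 |
| 23.4% | 0.80 × 0.766 | 61.3% | 18.7 |
| 24.6% | 0.80 × 0.754 | 60.3% | 19.7 |

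Only deaths count as failures here, and every survivor is taken as assessed. If non-implanted subjects also count as failures, multiplying 80% by the Step 2 shares gives 0.80 × 0.901 = 72.1% to 0.80 × 0.671 = 53.7%. Mitral surgery is not counted in any of these figures.

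**Step 4. Effect on a mean change**

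Let S be the survivors' baseline mean. The baseline mean of all subjects is (1 − m) × S + m × (S − d) = S − m × d. Subtracting it from the survivors' 1-year mean adds m × d to the survivors' true change.
- m = 6.3%, d = 5 to 20: 0.3 to 1.3 points
- m = 23.4%, d = 5 to 20: 1.2 to 4.7 points
- m = 24.6%, d = 5 to 20: 1.2 to 4.9 points
- d = 0: zero

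With paired change (same subjects at both visits) this term is zero for any d.

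**The case against.** The strongest reply is that the visible SAP does not commit to an unpaired comparison. It defines no change-from-baseline analysis, and SAP 2.2.1 defers the layout to table mockups that are not visible. Applied to a change score, an available-data rule would naturally use complete pairs. This stands: the excess in Step 4 is conditional, and hidden text may already remove it.

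Next, the percentage among those assessed and the share of all subjects alive in class I/II are different quantities, and each is correct for its own question. Mortality and early terminations are reported, n is shown for continuous variables, no hypothesis is tested, and the 1-year outcomes are descriptive rather than primary. This lowers the stakes. It does not settle the matter, because a separate death table does not change a percentage computed among attendees, and the reader cannot combine the two without knowing who was non-implanted, withdrawn or not assessed.

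The 23.4% comes from a high-risk arm, whereas exclusion criterion 5 removes subjects not expected to live through the 12-month follow-up. That is fair, and the lower mortality may be nearer.

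A reader might also infer that the rule distorts every analysis, including freedom from MAE at 30 days. The documents do not support that. APS has its own rule for death before discharge, SAP 2.2.3 censors time-to-event variables, and the analysis method for the primary endpoints is redacted. No claim about 30-day MAE can be made.

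**Conclusion.** The point holds for the visit-based 1-year summaries. As the visible text stands, they describe subjects alive, implanted and assessed, while baseline is summarised for all enrolled.

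The direction probably favours the device, since death and failed implantation are poor outcomes that leave the 1-year summary. The size is not shown. The 5 to 20 percentage-point gap rests on an assumed 80% and on mortality borrowed from other cohorts. The 0 to 4.9 KCCQ points rest on an assumed baseline deficit and on an unpaired comparison.

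Two stronger readings are tempting. One is that the plan compares survivors with a baseline that includes those who later die; the visible text neither states nor rules out pairing. The other is that benefit is demonstrably overstated; that would need data on how decedents differ, beyond the two small series. Calling the results survivors-only would also be incomplete, because non-implanted, withdrawn and unassessed subjects drop out too.

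This is a cheap improvement to a stated rule.

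**What to change.** In SAP 2.8 and 2.3.2:

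- **(a) Paired change.** Report change in KCCQ and six-minute walk as within-subject change, with the baseline mean restated for the same subjects. Confirm that baseline walk distance is captured: it is in Protocol Table 1 but not in the baseline data list of Protocol 11.4.
- **(b) Accounting.** At each visit, show the numbers alive, dead, non-implanted, withdrawn and missing.
- **(c) Whole-population summaries.** Beside the observed-case percentages, report two 1-year outcomes: alive without mitral surgery and in NYHA I/II; and alive without mitral surgery and with MR 2+ or less. Use the whole AP population as denominator. Count deaths and mitral surgery as failures. Count non-implanted subjects as failures in AP; they are absent from the IP version. Show living subjects with missing assessments under best-case and worst-case assignment.

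Protocol 5.5 keeps vital status after withdrawal, so deaths can be counted. The cost is a few extra tables from data the protocol already schedules, and 1-year percentages that look less favourable. If the mockups or redacted text already cover any of this, a cross-reference in SAP 2.8 is enough for that part.
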